12.2 General Methodology for Other Safety Data

Unless otherwise specified, tables, graphs and listings will be based on the APES (Open Label Period) and the APRS (Double-Blind Treatment Period).

All tables and graphs will be presented by inclusion source (Open Label Period) and treatment group (Double-Blind Treatment Period).

All safety endpoints will be reported for the 12-week Open Label Period and the 26-week Double-Blind Treatment Period separately.

The denominators for the summaries of a given variable will be based on the number of patients with non-missing values at a given visit or during the assessment period.

Descriptive statistics for the safety variables, both absolute values and changes from baseline, will be presented by visit and for the last assessment. All available post-baseline assessments (including data collected at unscheduled visits) will be included in the identification of the last assessment. With respect to baseline, the definition as presented in [section 4.1](#) will be used.

The number and percentage of patients with at least one potentially clinically significant (PCS) value at any post-baseline assessment time point will be summarized by variable. All available assessments will be included in the evaluation of PCS values.

The number and percentage of patients with values out-of-reference range and/or PCS range will be summarized by variable, visit, and last post-baseline assessment.

For patients with post-baseline PCS values, listings will be provided including all the values for those patients for the variable, with flagging of PCS values and out-of-reference-range values.

The PCS values relating to the paediatric population in this study will be applied.

Lundbeck standard criteria for identifying PCS values will be used.

12.3 Clinical Safety Laboratory Test Data

The clinical safety laboratory tests that are evaluated at baseline and post-baseline are included in the panel below.

Panel 4 Clinical Safety Laboratory Tests

Haematology	Clinical Chemistry	Urine
haemoglobin erythrocyte count total leucocyte count neutrophils ^a eosinophils ^a basophils ^a lymphocytes ^a monocytes ^a thrombocyte count	total bilirubin conjugated bilirubin alkaline phosphatase alanine aminotransferase aspartate aminotransferase gamma-glutamyl transferase creatinine urea nitrogen sodium potassium calcium (total) albumin estradiol [girls only] luteinising hormone [LH] follicle-stimulating hormone [FSH]) prolactin [PROLCTN] glucose low density lipoprotein high density lipoprotein triglycerides cholesterol (total)	protein (dipstick) glucose (dipstick) blood (dipstick)

Absolute and change from baseline in clinical safety laboratory tests will be summarized per treatment period. For the Open Label Period results will be presented per inclusion source and

overall, whereas for the Double-Blind Treatment Period the results will be summarized per treatment group and in total.

Urine results (dipstick) will be listed only. The microscopy results will be listed for patients with findings by assessment time point.

In case of any pregnancies these will be listed.

PCS values on laboratory tests will be flagged and summarized for the Open Label Period and Double-Blind Treatment Period as described in [section 12.2](#).

12.4 ECG, Vital Signs and Weight

Results on blood pressure, pulse rate, height and weight will be presented as described in [section 12.2](#).

The results from the central ECG readings will include the RR, PR, QRS, QT, QTc, and QTcF intervals. All of the ECG parameters will be summarized as described in [section 12.2](#).

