 - AEs, absolute and change from baseline in clinical safety laboratory tests (estradiol for girls, LH, FSH), Tanner staging, ECG, and effects on menstrual cycle, vital signs, height, weight, and ECG parameters will be summarized, and observed potentially clinically significant (PCS) safety laboratory test values will be flagged and summarized. GBI scores (using the 10-item mania subscale), and C-SSRS scores will be summarized using descriptive statistics.
 - AEs and other safety endpoints will be reported separately for the 12-week open-label period and the 26-week double-blind period.
- Patient disposition and demographics will be summarized using descriptive statistics.

Testing Strategy

[figure not shown]
Not applicable

Sample Size Considerations

The calculation of power is based on a log-rank test for the time to relapse at a one-sided 5% level of significance using SAS® Proc Power. A sample size of 80 randomized patients (40 patients per treatment group) will provide at least 80% power to find a difference between vortioxetine and placebo as statistically significant, when expecting cumulative relapse rates at 0.42 and 0.69 over 26 weeks, respectively, corresponding to a hazard-ratio of 2.15.

It is anticipated that approximately 60% of *de novo* patients enrolled into the open-label period will qualify for the double-blind study period. One-hundred fifty (150) patients are estimated to be enrolled into the study (depending on number and randomization rate of *de novo* and rollover patients).

Panel 1 Study Design

* Patients in remission (CDRS total score ≤ 28) at the two last visits in the open-label treatment period / Study 12712A OR with an adequate clinical response ($\geq 50\%$ reduction in the CDRS-R total score compared to the baseline score and a CDRS-R total score ≤ 35) at the two last visits in the open-label treatment period

**Relapse: CDRS-R total score of ≥ 40 with a history of 2 weeks of clinical deterioration, or a clinical deterioration that in the investigator's opinion warrants alteration of treatment to prevent full relapse

Panel 2 Study Procedures and Assessments – Open-label Period for *de novo* Patients and Rollover Patients from Study 12709A

Visit Name	Open-label Period								Randomization	Withdrawal ^d	Safety Follow-up ^e
	Screening ^a only de novo	Baseline ^b de novo	Baseline ^c 12709A rollover	3	4	5	6	7			
Visit Number	1	2	2	3	4	5	6	7	8		
Day/End of Week	d-5/d-15	0	0	W1	W2	W4	W8	W10	W12		W16

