
Safety Objectives
 
 to evaluate long-term safety and tolerability of vortioxetine in paediatric patients with MDD 	
Safety Endpoints
 
 adverse events absolute values and changes from baseline in clinical safety laboratory test values (including estradiol [girls only], and luteinising hormone [LH], follicle-stimulating hormone [FSH]), vital signs, height, weight, Tanner staging, electrocardiogram (ECG) parameter values. Effects on menstrual cycle will be assessed. potentially clinically significant clinical safety laboratory test values, vital signs, weight changes, and ECG parameter values Columbia-Suicide Severity Rating Scale (C-SSRS) score General Behaviour Inventory (GBI) using the 10-item mania subscale (parental version)

3 Study Design

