16.8.10 Analysis of Other Safety Endpoints

Absolute and change from baseline in clinical safety laboratory tests (estradiol for girls, LH, FSH), Tanner staging, and effects on menstrual cycle, vital signs, height, weight, BMI and ECG parameters will be summarized by treatment group. Potentially clinically significant (PCS) safety laboratory test values will be flagged and summarized.

GBI scores (using the 10-item mania subscale), and C-SSRS scores will be summarized using descriptive statistics.

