3.2 Double-Blind Treatment Period

Double-Blind Treatment Period (for all randomized patients)

- Patients who fulfil the randomization criteria and do not meet any of the withdrawal criteria during the Open Label Period or at the time of randomization will be randomly assigned via a centralized randomization system to receive vortioxetine or placebo in a 1:1 ratio. Randomization will be stratified by patient inclusion sources (*de novo* patients, rollover patients from 12709A, or from 12712A).
- Patients randomized to vortioxetine will continue on their final dose from the Open Label Period or the dose they had on their last visit in Study 12712A, as applicable.
- The maximum duration of the Double-Blind Treatment Period will be 26 weeks.
- Patients who relapse during the Double-Blind Treatment Period must be withdrawn from the study. The criterion for a relapse is a CDRS-R total score of ≥ 40 with a history of 2 weeks of clinical deterioration, or a clinical deterioration that in the investigator's opinion warrants alteration of treatment to prevent full relapse.

A Safety Follow-up Visit will be performed 4 weeks after withdrawal or completion of the Double-Blind Treatment Period.

Panel 2 Schedule of Study Design

* Patients in remission (CDRS total score ≤ 28) at the two last visits in the Open Label period / Study 12712A OR with an adequate clinical response ($\geq 50\%$ reduction in the CDRS-R total score compared to the baseline score and a CDRS-R total score ≤ 35) at the two last visits in the Open Label period

**Relapse: CDRS-R total score of ≥ 40 with a history of 2 weeks of clinical deterioration, or a clinical deterioration that in the investigator's opinion warrants alteration of treatment to prevent full relapse

4 Definitions

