7.2 Withdrawals

The number of patients who withdrew from the Open Label Period will be summarized by *de novo* patients, rollover patients from Study 12709A and total. The number of patients who withdrew from the Double-Blind Treatment Period will be summarized by treatment group and total. The primary reason for withdrawal as well as all reasons for withdrawal will be presented per period.

Patients who withdrew from the study will be listed and the listing will include the number of days in the study until withdrawal from the study, the number of days on IMP, the primary reason for withdrawal, and all reasons for withdrawal.

8 Demographics and Baseline Characteristics

Summary tables on demographic and baseline characteristics will be presented for both the Open Label Period and the Double-Blind Treatment Period separately. The baseline characteristics for the Open Label Period will be based on the APES and will be presented for *de novo* patients, rollover patients (from Study 12709A) and overall.

For the Double-Blind Treatment Period the summary tables on demographics will be based on the FAS and results will be presented per treatment group (vortioxetine and placebo) and in total.

Demographics (sex, age, ethnicity and race), baseline characteristics (height, weight and BMI), disease characteristics and baseline efficacy variables will be summarized.

The following baseline (randomization) efficacy variables will be summarized:

CDRS-R total score

CGI-S score

PQ-LES-Q scores (total score and overall score (item 15))

Disease characteristics will include MDE history (MDD history, including number of MDEs, duration of current episode, treatment type (psychotherapy / pharmacotherapy) for MDD. In addition, MDD treatment will be summarized.

Medical history from the Medical History eCRF page will be coded with medical dictionary for regulatory activities (MedDRA) version 19.0 or above. All medical histories, data on major depressive disorder history and treatment, the family psychiatric history and the history of stimulant medication will be listed.

9 Recent and Concomitant Medication

Recent and concomitant medication will be coded using the WHO Drug Dictionary (WHO Global B3 Mar 2020).

Medications will be classified according to the start and stop time and summarized by anatomical therapeutic chemical (ATC) code, generic drug name:

- medication discontinued prior to first dose of IMP in Open Label Period

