11.6 Pharmacokinetic Analyses

The pharmacokinetic analyses will be described in a separate population PK analysis plan.

12 Safety

The safety analyses will be performed for each period, based on the APES and the APRS. Unless otherwise specified the tables and listings of the Open Label Period are based on APES. The tables and listings of the Double-Blind Treatment Period are based on the APRS.

All safety endpoints will be reported for the 12-week Open Label Period and the 26-week Double-Blind Treatment Period separately. The results of the safety analysis of the Open Label Period will be presented by patient group (*de novo* patients and rollover patients from Study 12709A) and overall.

The results of the safety analyses of the Double-Blind Treatment Period will be displayed by treatment group and overall.

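### SAP 12.4 omits, without explanation, the by-arm BMI summary planned in protocol 16.8.10, and the SAP has no age- and sex-standardized growth measure for 7-11-year-olds (minor; cheap to fix)

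*SAP*

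**What the plan says.** Protocol 16.8.10, which covers absolute values and changes from baseline, says "vital signs, height, weight, BMI and ECG parameters will be summarized by treatment group". SAP 12.4 says "Results on blood pressure, pulse rate, height and weight will be presented as described in" section 12.2, so its list is blood pressure, pulse rate, height and weight, with ECG handled separately. The SAP's only planned use of BMI is in section 8: "baseline characteristics (height, weight and BMI), disease characteristics and baseline efficacy variables will be summarized".

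The BMI commitment stands in protocol 16.8.10 alone. The synopsis gives the same list without it ("vital signs, height, weight, and ECG parameters will be summarized"), and the endpoint panels of both documents name height and weight but not BMI. Weight change is also an endpoint through the PCS item in protocol Panel 4: "potentially clinically significant clinical safety laboratory test values, vital signs, weight changes, and ECG parameter values".

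For the variables it lists, SAP 12.2 states: "Descriptive statistics for the safety variables, both absolute values and changes from baseline, will be presented by visit and for the last assessment". SAP section 12 adds: "The results of the safety analyses of the Double-Blind Treatment Period will be displayed by treatment group and overall". Patients are allocated "to receive vortioxetine or placebo in a 1:1 ratio". SAP 4.1 sets the safety baseline at the start of open label for de novo and 12709A patients, and at randomization for 12712A patients.

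**The concern.** A planned safety summary disappears between protocol and SAP with no stated reason. The protocol's own account of the adolescent study (section 1.1.3.3) reports changes in weight, BMI and height together, so the sponsor has used this output in the same programme.

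What remains is change in kilograms and centimetres in children who are growing. Long-term safety in children is a stated objective, and height and weight are named safety endpoints. Where there is no concurrent control, or where follow-up time differs between groups, part of any observed change is simply elapsed time. A reader of those tables could take growth for drug-related weight gain, or miss a slowing of height.

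**Working it through.** **Text comparison**

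| Place | Height, weight | BMI change by arm | Age/sex-standardized |
|---|---|---|---|
| Protocol 16.8.10 | yes | yes | no |
| Protocol synopsis | yes | not named | no |
| SAP 12.4 with 12.2 | yes, absolute and change | not listed | no |
| SAP section 8 | baseline only | baseline only | no |

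The plan gives no figure on this point to reproduce. The growth rates below are assumptions, not in the documents: 2-4 kg/year and 5-6 cm/year, with 52.18 weeks per year.

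**1. Open-label period (12 weeks, no control)**
- Weight: 2 × 12/52.18 = 0.46 kg; 4 × 12/52.18 = 0.92 kg.
- Height: 5 × 12/52.18 = 1.15 cm; 6 × 12/52.18 = 1.38 cm.
- As a share of an assumed body weight of 25-35 kg: 0.46/35 = 1.3% to 0.92/25 = 3.7%.

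**2. Last-assessment change in the double-blind period**

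SAP 3.2 withdraws patients at relapse, and SAP section 14 plans relapse rates of 0.42 (vortioxetine) and 0.69 (placebo) over 26 weeks. With exponential relapse times and no other dropout, the weekly hazard is h = −ln(1 − p)/26 and mean time on study is p/h.
- Vortioxetine: 0.42 / (−ln 0.58 / 26) = 20.0 weeks.
- Placebo: 0.69 / (−ln 0.31 / 26) = 15.3 weeks.
- Gap: 4.73 weeks.

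Normal growth in the gap:
- Weight: 2 × 4.73/52.18 = 0.18 kg to 4 × 4.73/52.18 = 0.36 kg.
- Height: 5 × 4.73/52.18 = 0.45 cm to 6 × 4.73/52.18 = 0.54 cm.

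The longer-followed arm is vortioxetine, so the gap would look like weight gain on drug and would offset any slowing of height.

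**3. By-visit change in the double-blind period**

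Elapsed time is essentially equal between arms, so expected growth cancels. Protocol Panel 3 schedules height and weight only at randomization, Week 10 and Week 26 or withdrawal. Under the planned rates, 40 × 0.58 = 23 and 40 × 0.31 = 12 patients reach Week 26 without relapse, before other dropout. The comparison is valid in kind but imprecise, and it is restricted mainly to patients still on study.

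**4. Mixed baselines**

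At Week 26, change covers 12 + 26 = 38 weeks for de novo and 12709A patients, and 26 weeks for 12712A patients. For the first group it includes 12 weeks on vortioxetine in both arms. The extra 12 weeks are worth 0.46-0.92 kg and 1.15-1.38 cm, as in step 1. Stratified randomization balances the sources across arms in expectation, so this mainly adds spread and leaves the mean change without a single time span.

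**5. What raw BMI would add**

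Three assumed children, followed for 26 weeks:

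| Height, weight | Growth per year | Weight gain | BMI change |
|---|---|---|---|
| 1.22 m, 23 kg | 6 cm, 2.5 kg | 1.25 kg (5.4%) | 15.45 to 15.52 (0.4%) |
| 1.33 m, 30 kg | 5.5 cm, 3 kg | 1.49 kg (5.0%) | 16.96 to 17.09 (0.8%) |
| 1.43 m, 36 kg | 6 cm, 4 kg | 1.99 kg (5.5%) | 17.60 to 17.83 (1.3%) |

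Raw BMI moves much less with normal growth than weight does, but it still moves, and it does not isolate a height effect. Restoring it closes the mismatch and only part of the growth problem.

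**The case against.** The strongest reply is that randomization already handles growth. Placebo is concurrent, results are shown by arm and by visit, and changes are planned as well as absolute values. This stands for by-visit double-blind comparisons. A reader might infer from the BMI omission that a weight or growth effect cannot be told from normal growth at all; the documents do not support that.

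A reader might also infer that PCS weight flags will fire on normal growth, pointing to 38 weeks of gain: 2-4 kg/year is 1.46-2.91 kg, or 4.2%-11.7% of 25-35 kg. That does not follow either. The PCS criteria are not in the documents, and SAP 12.2 says paediatric values apply. The 38-week span ends in the placebo-controlled period and applies only to de novo and 12709A patients; the uncontrolled span is 12 weeks, where the same assumption gives 1.3%-3.7%.

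Other points also stand. BMI is not a named endpoint. It can be derived at any time from data already collected. Default listings carry sex, age and baseline weight (SAP section 6), and weight changes judged clinically significant become adverse events (protocol 9.4.4). Neither document promised z-scores, so those are a suggested improvement, not the repair of a broken commitment.

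None of this explains the missing BMI summary, and the placebo arm does not help the open-label tables or equalize follow-up at last assessment.

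**Conclusion.** The BMI mismatch between protocol 16.8.10 and SAP 12.4 is real and unexplained, and no growth standardization is planned. It is a reporting gap of minor severity: no data are lost and the primary analysis is unaffected.

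Interpretation suffers in the open-label tables, the last-assessment summaries and the double-blind changes with mixed baselines. The sizes rest on assumed growth rates. The follow-up gap further assumes the planned relapse rates, exponential relapse times and no other dropout; if relapse and other withdrawal were alike in the two arms, it would vanish.

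**What to change.** 1. Add BMI, absolute and change from baseline, by arm, to SAP 12.4; if it is left out on purpose, say why.
2. Add z-scores for age and sex for height, weight and BMI against one named growth reference. Report change in z-score alongside the raw summaries, for both periods.
3. For the double-blind period, also report these changes from randomization for all inclusion sources.
4. Keep the sponsor's paediatric PCS criteria as planned.

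Cost: SAP wording and a derivation from height, weight, sex and age, all already collected. A growth reference has to be chosen and named. Protocol 9.1.1 collects full birth date only where local rules permit, so z-scores will be coarser elsewhere.

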12.5 Other Safety Endpoints

Tanner staging is a scale for assessing physical development and sexual maturity during onset and progress of puberty. The scale includes 5 stages of pubertal changes (called Tanner stages) separate for males and for females.

Data on Tanner staging and menstrual cycle (age of menarche, length of the menstrual cycle and menstrual cycle regularity) will be listed only.

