8.4 Randomization Visit (Visit 8)

The double-blind period starts with the Randomization Visit (8) at Week 12. Patients who fulfil the randomization criteria (section 5.4) will be randomly assigned via a centralized randomization system to receive vortioxetine or placebo in a 1:1 ratio.

Patients rolling over from Study 12712A need to fulfil inclusion/exclusion criteria detailed in sections 5.3. At the Randomization Visit, *de novo* patients and rollover patients from Study 12709A undergo evaluation of randomization criteria, and evaluation of efficacy and safety assessments as per [Panel 3](#). Patients who do not meet the randomization criteria will be withdrawn from the study and complete an early withdrawal visit.

For 12712A-patients, last available values from assessments and procedures (efficacy/safety, and use of concomitant medication) performed at either Visit 7 (Week 8) and/or Visit 8 (Week 10), or Visit 9 (Week 12) in Study 12712A will be the Randomization Visit values for this study. For patients who rollover at Visit 7 or Visit 8, weight, height, Tanner staging, menstrual cycle, and examinations should be done at the Randomization Visits (detailed in [Panel 3](#) and section 11.1.2).

The schedule of assessments during the Double-blind Period is described in [Panel 3](#).

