16.3 Descriptive Statistics

In general, summary statistics (n, arithmetic mean, standard deviation, median, lower and upper quartiles, minimum and maximum values) will be presented for continuous variables. Counts and, if relevant, percentages will be presented for categorical variables.

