
Safety Objectives
 
• to evaluate long-term safety and tolerability of vortioxetine in paediatric patients with MDD	
Safety Endpoints
 
• adverse events• absolute values and changes from baseline in clinical safety laboratory test values (including estradiol [girls only], and luteinising hormone [LH], follicle-stimulating hormone [FSH]), vital signs, height, weight, Tanner staging, electrocardiogram (ECG) parameter values. Effects on menstrual cycle will be assessed.• potentially clinically significant clinical safety laboratory test values, vital signs, weight changes, and ECG parameter values• Columbia-Suicide Severity Rating Scale (C-SSRS) score• General Behaviour Inventory (GBI) using the 10-item mania subscale (parental version)

3 Study Design

This is an interventional, multi-national, multi-site, randomized, parallel-group, placebo-controlled, relapse-prevention study in paediatric patients with MDD from 7 to 11 years of age.

The study consists of a 12-week, open-label, flexible-dose treatment period with vortioxetine followed by a 26-week, randomized, Double Blind, fixed-dose, placebo-controlled relapse-prevention period.

The study population will include *de novo* patients as well as rollover patients from other paediatric vortioxetine studies (Studies 12709A and 12712A), who, in the investigator's opinion, could benefit from continued treatment with vortioxetine. To reach 80 randomized patients, approximately 150 patients recruited, either as *de novo* patients or rollover patients from Study 12709A and 12712A, are estimated to be enrolled into the study.

De novo patients

- Patients meeting eligibility criteria for *de novo* patients will be enrolled in the 12-week, open-label, flexible-dose treatment period.

Rollover patients from Study 12709A (enrolled to the Open Label Period)

- Patients may participate in the present study after completion of the randomized, 8-week, Double Blind, placebo-controlled treatment period of Study 12709A.
- Eligible patients will be enrolled in the 12-week, open-label, flexible-dose treatment period.
- The Baseline Visit of this study (Study 13546A) will take place at the same visit as Visit 12 (Completion Visit) of Study 12709A. Participation in Study 12709A is considered completed when all assessments required at Visit 12 are completed.

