4.3 Definition of Withdrawal

The patients who withdraw from the Open Label Period or the Double-Blind Treatment period will be described as *withdrawn from the study*. The remaining patients will be described as *completed the study*.

5 Analysis Sets

The following analysis sets will be used to analyze and present the data:

all-patients-enrolled (APES) – all-patients-enrolled to the 12-week Open Label Treatment Period who took at least one dose of IMP

all-patients-randomized set (APRS) – all patients randomized to the 26-week Double-Blind Treatment Period

full-analysis set (FAS) – all patients randomized to the 26-week Double-Blind Treatment Period who took at least one dose of Double Blind IMP

The efficacy analyses will be based on the FAS and the safety analyses will be based on the APES (for *de novo* and 12709A rollover patients) and the APRS (for 12712A rollover patients).

The patients and data will be classified into the analysis sets according to the definitions above during a *Classification Meeting* after the study database has been released, but before the blind has been broken.

6 Descriptive Statistics

In general, summary statistics (n, arithmetic mean, standard deviation, median, minimum and maximum values) will be presented for continuous variables. Counts and, if relevant, percentages will be presented for categorical variables. The denominator for the percentage calculation will be noted.

Unless otherwise specified, data listings will include enrolment source, site, treatment group, patient screening number, sex, age, race, and baseline weight.

7 Patient Disposition

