12.5.2 General Behavior Inventory (GBI) 10-Item Mania Scale

The GBI 10-item mania scale is a parent- and patient-rated scale designed to screen for manic symptoms in children and adolescents. The ten items are rated on a 4-point scale from 0 (never or hardly ever) to 3 (very often or almost constantly). The total score ranges from 0 to 30, with higher scores indicating greater pathology. Only the parent-rated scale will be used in this study.

Summary statistics on the total score, absolute scores as well as changes from baseline for each visit as well as the latest assessment will be presented per study period and inclusion source (Open Label Period) and treatment group (Double-Blind Treatment Period).

13 Interim Analyses

No interim analyses will be performed.

14 Sample Size Considerations

The calculation of power is based on a log-rank test for the time to relapse at a one-sided 5% level of significance using SAS Proc Power. A sample size of 80 randomized patients (40 patients per treatment group) will provide at least 80% power to find a difference between vortioxetine and placebo as statistically significant, when expecting cumulative relapse rates at 0.42 and 0.69 over 26 weeks, respectively corresponding to a hazard-ratio of 2.15. The assumption of relapse rates (42% and 69% over 6 months for vortioxetine and placebo, respectively) is based on observed rates from a similarly designed relapse-prevention study of fluoxetine in pediatric patients with MDD who had an adequate response after 12 weeks of acute treatment¹.

It is anticipated that approximately 60% of *de novo* patients enrolled into the Open Label Period will qualify for the Double-Blind Treatment Period. To achieve 80 randomized patients, 150 patients are estimated to be enrolled into the study (depending on number and randomization rate of *de novo* and rollover patients).

15 Statistical Software

The statistical software used will be SAS[®], Version 9.4 or later.

16 Details on Data Handling

An LOCF approach will be used for the Double-Blind Treatment Period of the following scales: CDRS-R, PQ-LES-Q, CGI-I and CGI-S.

The LOCF approach will only be used for the total scores (if applicable). The last usable assessment in the Double-Blind Treatment Period (excluding the randomization assessment) will be used to impute missing values for the LOCF. See also section [Section 16.1.3](#) for the handling of missing data related to COVID-19.

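### SAP 12.5 only lists Tanner staging and menstrual data, although protocol 16.8.10 says both will be summarized by treatment group, and the SAP gives no reason

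*SAP*

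**What the plan says.** Protocol 16.8.10 covers absolute values and changes from baseline, and its list ends: "Tanner staging, and effects on menstrual cycle, vital signs, height, weight, BMI and ECG parameters will be summarized by treatment group". The protocol synopsis also says these data will be summarized. Protocol 16.8.8 requires every safety endpoint to be reported separately for the open-label and double-blind periods.

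The SAP carries the endpoint forward. In its Panel 1 (section 2), the entry for absolute values and changes from baseline includes "vital signs, height, weight, Tanner staging, electrocardiogram (ECG) parameter values. Effects on menstrual cycle will be assessed".

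SAP 12.5 then sets the presentation: "Data on Tanner staging and menstrual cycle (age of menarche, length of the menstrual cycle and menstrual cycle regularity) will be listed only". No explanation accompanies this.

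**The concern.** The protocol assigns the SAP the task of describing the planned analyses in more detail (protocol 16.11). Here the SAP removes a planned analysis, and it does so for an endpoint that its own Panel 1 still lists.

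What is at stake is descriptive safety reporting. Sexual maturation is a natural question for a drug given for up to 38 weeks (12 open-label plus 26 double-blind) to children of this age. Under the SAP as written, a reader of the tables would not see how the arms compared on pubertal stage at randomization, how many children moved up a stage in each arm, or whether menstrual findings differed. Answering any of these would mean counting by hand from a listing.

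**Working it through.** No alpha, power or effect size enters this point. The check is whether any part of the SAP restores what section 12.5 removes, and whether the data for a summary are collected.

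**Does another SAP section supply the summary?**

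- *Section 8 (baseline tables):* summarizes demographics, height, weight, BMI, disease characteristics and baseline efficacy scores. Tanner stage and menarche are not included.
- *Section 12.2 (general rule for other safety data):* calls for descriptive statistics by visit for absolute values and changes. Read alone, it could cover Tanner staging. But sections 12.3 and 12.4 refer back to 12.2 for their variables, while 12.5 gives a specific contrary instruction for Tanner and menstrual data. The specific sentence governs.
- *Section 12.3:* summarizes laboratory tests by treatment group, including LH, FSH and, for girls, estradiol. These relate to puberty but report neither stage nor menstrual outcome.
- *Section 12.4:* covers ECG, vital signs, height and weight.
- *Section 16.1.2:* mentions Tanner staging only to say that missing values are not imputed.

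No section restores it. The protocol plans a summary by arm, the SAP plans a listing, and the SAP states no reason.

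**Are the data collected?**

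- The double-blind schedule (protocol Panel 3, SAP Appendix II B) marks Tanner staging and menstrual cycle at Visit 8 and at completion or withdrawal.
- Protocol 8.4 says that at Visit 8 de novo and 12709A patients "undergo evaluation of randomization criteria, and evaluation of efficacy and safety assessments as per" Panel 3. It also requires staging at randomization for 12712A patients who enter at that study's Visit 7 or Visit 8.
- The open-label schedule (protocol Panel 2, SAP Appendix II A) marks staging at screening for de novo patients and at the baseline visit for 12709A patients. It shows one later mark, apparently at withdrawal and not at Visit 8. The extracted table is broken, so this is not certain.

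Staging at Visit 8 is therefore the likelier reading for de novo and 12709A patients, but Panel 2 leaves some doubt. A summary that uses Visit 8 should be conditional on the staging having been done.

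**How much is involved?** With 80 randomized patients and at most two stagings each in the double-blind schedule, a reader working from the listing would face at most 80 × 2 = 160 records. That is inconvenient, but feasible.

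**The case against.** The case for leaving the SAP alone has real substance.

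- *The information is not lost.* By default, SAP section 6 puts treatment group, sex and age in every listing. A reader might infer that the between-arm result cannot be obtained. The documents do not support that: it can be counted from the listing.
- *The table templates are elsewhere.* SAP section 1 places them in a separate document. A reader might infer that no such table will ever be produced, but that is established only for the SAP text. A template containing one would, however, contradict section 12.5.
- *Cells will be small.* Menstrual data in girls of this age are likely to be sparse, and few children may be beyond Tanner stage 1. A listing can be a defensible display, but then the SAP should say so.
- *Related data are tabulated.* Height, weight, LH, FSH and estradiol still receive by-arm summaries.

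All of this stands and limits the size of the point. None of it explains a departure from the protocol made without comment.

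A stronger argument is also tempting. Under SAP 3.2, "Patients who relapse during the Double-Blind Treatment Period must be withdrawn from the study", and SAP section 14 plans on "expecting cumulative relapse rates at 0.42 and 0.69 over 26 weeks" for vortioxetine and placebo respectively. Placebo children would then tend to be restaged sooner, and a reader might infer that hand counts from the listing would mislead. But the same unequal follow-up would affect a summary table of stage change equally, so it is not a consequence of listing. Nor does the possibility of chance imbalance in pubertal stage between two arms of 40 measure any harm from omitting a table.

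**Conclusion.** The inconsistency is real and the concern holds in limited form. SAP 12.5 contradicts protocol 16.8.10 and leaves an endpoint named in SAP Panel 1 without a by-arm summary in the SAP text. The SAP does not justify the change.

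Severity is minor. Two descriptive summaries, Tanner stage and menstrual data, are affected; the data remain recoverable; and neither the primary analysis nor any efficacy result changes. The conclusion rests on two readings: that the specific sentence in 12.5 overrides the general rule in 12.2, and that the unseen table templates follow the SAP text.

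**What to change.** In SAP 12.5, replace the listing-only instruction with a descriptive summary and keep the listings as support.

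- *Double-blind period:* counts by Tanner stage, by sex and treatment group, at randomization (where staged) and at completion or withdrawal. Show change from the SAP 4.1 baseline, which is what the protocol promises, and the shift from Visit 8 where that staging is available.
- *Open-label period:* the same display by inclusion source, as protocol 16.8.8 requires reporting for each period.
- *Menstrual data:* a short summary by treatment group of menarche, cycle length and regularity in girls, where numbers allow.

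If the sponsor prefers listings because numbers are too small, the SAP should say so and identify this as a change from the protocol.

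The cost is one or two extra descriptive tables from data already scheduled for collection. The drawback is small cells. The documents do not give the share of children at Tanner stage 2 or higher. Purely as an assumption, a share of 10% to 40% gives 40 × 0.10 = 4 to 40 × 0.40 = 16 such children per arm, or about 2 to 8 per sex and arm if half are girls. At the low end the table would be sparse but still readable as counts.
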